1.3.4.1 Inclusion criteria

The complexity of the revised Rome criteria for functional constipation²² militates against their use in screening for chronic constipation. Moreover, newly incident cases of constipation, especially amongst older adults, should be investigated to determine the underlying cause of the constipation and to eliminate more serious problems²³ before laxatives are prescribed.

This trial will therefore identify and recruit only 'prevalent' cases, defined in terms of those prescribed laxatives three or more times in the previous 12 months. Participants meeting this criterion will be identified from general practice computerised patient records using an electronic 'query' to interrogate repeat prescribing databases. It is recognised that the relapsing and remitting nature of constipation means that not all patients thus identified will be constipated (by objective or subjective criteria) at any given time. Eligible participants who have given informed consent will be invited to complete a baseline assessment during which current bowel function and perceptions of whether constipated will be elicited; these baseline data will be included as co-variables in our analysis (1.3.7).

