1.3.5.3 Methods of data collection

1.3.5.3.1 Base-line assessment (W⁰)

Prior to any assessments being conducted, each participant will speak on the telephone with a member of the research team and be invited to discuss any aspect of participation in the study they wish. Once informed consent has been obtained the baseline assessment will be conducted. This assessment will include a short telephone structured interview and a short self completion questionnaire. Current bowel function (based on Rome criteria), fluid and fibre intake and patients' self-perceptions of whether they are currently constipated and levels of anxiety and depression²⁸ will be elicited and data on activities of daily living²⁹, condition-specific quality of life and laxative use (both prescribed and over the counter) will be collected. A weekly structured self-completed diary will be distributed and explained. The person conducting the baseline assessment will notify practices that patients are ready to begin the intervention (as per protocol) and practices will make an appointment to see participants to start the intervention. In following this approach we minimise the risk of patients who have not given informed consent receiving the intervention as the intervention will only be delivered once a signed copy of the consent form is sent to the practice with the instruction to begin the intervention. At this first appointment, treatment per intervention protocol (1.3.5.4) will be initiated. Should patients decide to withdraw when they return to collect either their laxative prescription or for their diet and lifestyle appointment, the practice will notify the research team and all baseline assessment data and patient identification data will be destroyed or deleted from the study database.

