1.3.5.3.5 Medical records (W^{52})

Data pertaining to consultation rates and prescription of laxatives for all study participants for the twelve months post recruitment will be abstracted from medical records. This will be done practice-by-practice at the end of the data collection period. Trained research nurses will interrogate paper-based and computerised records and will enter data directly to a database on lap-top computer. The electronic query used to identify patients at the beginning of the trial will be adapted to capture data on laxative prescriptions. We have used these methods of data collection to good effect in previous similar studies.

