1.3.5.4 Participants' pathways through trial

		Activity
1		Potential participants identified from computerised practice databases using simple electronic query to flag individuals receiving prescriptions for constipation (3 or more in previous 12 months).
2		Initial screen by practice to identify clear exclusions.
3		Written invitation sent by practice (facilitated by research team) to patient to participate in study. Contact details form and pre-paid envelope included for patients wishing to join the study included. Research team to contact patient to answer questions and explain about process for informed consent. Consent form posted to patient with pre-paid envelope. Self completion questionnaire and pre-paid envelope also sent. Control patients will receive their diary (including pre-paid envelope) at this point.
4	W^0	When consent form is returned the telephone baseline interview will be conducted. patient advised to expect contact from practice to arrange 'intervention start' appointment.
5	W^1	Appointment at practice – laxative prescription issued or diet and lifestyle intervention initiated. All patient information and baseline data destroyed by research team if patient notifies practice of their wish to withdraw from study.
6	W^2	One week reinforcement phone call from nurse to patients randomised to personalised diet and lifestyle advice
7	W^{3-4}	Intervention fidelity measure – a small sample of patients in the standardised and personalised intervention arms of the trial will receive a short postal questionnaire to ask about the diet and lifestyle advice.
8	W^5	One month reinforcement phone call from nurse to patients randomised to personalised diet and lifestyle advice
9	W^{12}	Three month follow up outcome assessment (postal questionnaire) and collection of cost data and personal levels of success (telephone interview)
10	W^{26}	Six month follow up outcome assessment (postal questionnaire) and collection of cost data and personal levels of success (telephone interview)
11	W^{52}	Twelve month follow up outcome assessment (postal questionnaire & 1-week symptom diary). Review of practice notes to abstract data on consultation rates and prescription patterns.

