1.3.6.2 Patient identification and recruitment

Two methods of patient identification were considered: incident and prevalent cases. Consultation rate data²¹ indicate that there would be only a small number of incident cases per year in any one practice. Moreover, these incident cases would, at least initially, be subject to more intensive medical investigation²³, which would militate against inclusion in the trial. Finally, we are aware of experiences of differential rates of patient identification across active and control arms of previous cluster randomised trials (e.g. the UK BEAM trial) and the potential for selection bias that results from such differential rates. This risk is greater when incident cases are being identified, and when responsibility for identification lies with the clinician. For these reasons, only prevalent cases (1.3.4.1), which will be retrospectively identified through computerised records, will be considered.

The identification process will be through an independent interrogation of practice prescribing databases, and will therefore not be subject to influence by the participating clinicians. We believe that this approach will minimise selection bias.

To spread practice workload, patient recruitment in each practice will be spread over four months. It would not be practicable to identify all (i.e. across all 57 practices) potentially eligible patients prior to practice randomisation and patient contact. The reason for this is that bowel symptoms may fluctuate in patients and a patient identified as 'constipated' at a given point in time may no longer be 'constipated' several months later. We expect that the delivery of the intervention to practices will extend over 10 months. Initial eligibility of patients will be based on receipt of 3 or more prescriptions for laxatives in the preceding 12 months (1.3.4.1). If the patient identification query were to be run in all practices at the beginning of this 10 month period and patients thus identified were to be 'banked' until the intervention was delivered in a specific practice, some of those identified might no longer meet eligibility criteria, while others by then meeting eligibility criteria would not be considered for inclusion.

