1.3.7 Statistical analysis

Analysis will be on an intention-to-treat basis. No sub-group analyses are planned. The data will be analysed using mixed effects models, accepted practice for the analysis of data from cluster randomised trials³¹. Variation between practices and variation between patients nested within practices will be fitted as random effects. The difference between treatment strategies (i.e. the three arms of the trial will be fitted as fixed effects. Most of the outcome variables (e.g. quality of life scores, number of days with (or without) symptoms are continuous and will be analysed assuming a Normal error structure. The dependent variable in each model will be point of follow-up (three, six and twelve months outcomes for quality of life, symptoms and perceptions of bowel function; twelve months for consultation and prescription rates). For each patient, baseline data will be included as a co-variate. The mixed models will be used to generate interval estimates for the differences between alternative treatment strategies.

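### Record-based twelve-month outcomes have no planned like-for-like prior-year covariate, although the eligibility query already reads the prior year of laxative prescriptions

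*Protocol*

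**What the plan says.** **Outcomes and model.** Protocol section 1.3.7 fits mixed models at each follow-up point, including "twelve months for consultation and prescription rates". On adjustment it states: "For each patient, baseline data will be included as a co-variate".

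**Record window.** Section 1.3.5.3.5 states that data on consultations and laxative prescriptions "for the twelve months post recruitment will be abstracted from medical records". Table 2 and the last row of the pathway in section 1.3.5.4 also place this review once, at twelve months.

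**Eligibility query.** Section 1.3.4.1 defines prevalent cases as "those prescribed laxatives three or more times in the previous 12 months", and section 1.3.6.2 repeats the rule. Section 1.3.5.4 describes the tool as a "simple electronic query to flag individuals receiving prescriptions for constipation (3 or more in previous 12 months". Section 1.3.5.3.5 plans to use it again: "The electronic query used to identify patients at the beginning of the trial will be adapted to capture data on laxative prescriptions".

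**Baseline data.** Section 1.3.5.3.1 collects bowel function, fluid and fibre intake, perceived constipation, anxiety and depression, activities of daily living and condition-specific quality of life. It adds that "laxative use (both prescribed and over the counter) will be collected". Consultations are not on the list.

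**The concern.** A patient's own use in the previous year is the natural covariate for a count of prescriptions or consultations over the following year. The plan opens the records that hold it but abstracts only the year after recruitment.

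The outcomes concerned carry weight. Section 1.3.5.2 defines relapse by re-consultation or further laxative prescriptions, monitored through the medical records. Section 1.3.8.3 takes consultations and prescribed drugs for NHS costs from the same source, in a trial commissioned on cost-effectiveness.

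The design also leaves room for the arms to differ in prior use. Section 1.3.9 says that patients consent after their practice has been randomised. Section 1.3.3.1 names reluctance to give up medication as a threat to recruitment, and section 1.3.6.3 expects some patients in the diet and lifestyle arms to decline. If heavier laxative users decline more often in those arms, a prior-year count would show it and allow adjustment for it.

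This has to be settled in the protocol because it concerns which data are collected. A later analysis plan can choose among covariates, but it cannot adjust for consultations that nobody abstracted.

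**Working it through.** **Step 1. Which pre-recruitment values exist?**

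| Outcome at twelve months | Pre-recruitment value planned | Like-for-like? |
|---|---|---|
| Consultations (records) | None | No |
| Laxative prescriptions (records) | Patient-reported use at baseline; three-or-more flag from the query | No: the first differs in source and possibly in period and scale; the second is met by everyone recruited |
| Relapse and NHS cost | Only what the two rows above supply | No |
| Quality of life (primary) | Same instrument at baseline | Yes |

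The flag cannot act as a covariate because every participant satisfies it. The count behind it could.

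**Step 2. The plan's own figure.** Section 1.3.6.3 gives an effect of 0.3 SD, 90% power, 5% significance (taken as two-sided), an intra-class correlation of 0.04 and 25 patients per practice.

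- Patients per arm without clustering: 2 × ((1.960 + 1.282) / 0.3)² = 233.5
- Design effect: 1 + (25 − 1) × 0.04 = 1.96
- Practices per arm: 233.5 × 1.96 / 25 = 18.3, rounded up to 19, so 57 in total

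The stated 57 reproduces. It is set on quality of life and is not in dispute here.

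**Step 3. What a prior-year covariate would add.** The documents give no correlation r between prior-year and post-recruitment values, so a range is assumed, equal at patient and practice level. As an illustration, the design values from Step 2 are carried over to the record-based outcomes.

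- Unadjusted standard error of a pairwise difference, in SD units: √(2 × 1.96 / (19 × 25)) = 0.091
- Difference detectable with 90% power: (1.960 + 1.282) × 0.0908 = 0.294
- With adjustment, the variance is multiplied by 1 − r² and the standard error by √(1 − r²)

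| Assumed r | Variance left | Variance removed | Interval narrower by | SE | Detectable difference (SD) |
|---|---|---|---|---|---|
| 0 | 1.00 | 0% | 0% | 0.091 | 0.294 |
| 0.3 | 0.91 | 9% | 5% | 0.087 | 0.281 |
| 0.5 | 0.75 | 25% | 13% | 0.079 | 0.255 |
| 0.7 | 0.51 | 49% | 29% | 0.065 | 0.210 |

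**Step 4. Against the adjustment already planned.** The table compares with no adjustment, which is not what section 1.3.7 plans. Suppose the planned baseline data already reach a multiple correlation of 0.3, and adding the prior-year count raises it to 0.5. The variance ratio is then 0.75 / 0.91 = 0.82, a cut of 18% rather than 25%. If it rises to 0.7, the ratio is 0.51 / 0.91 = 0.56, a cut of 44% rather than 49%. These values are illustrative; the documents supply none.

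**Step 5. Imbalance.** If the arms differ in prior use by d SD, an unadjusted contrast shifts by about r × d, that is 0.3 to 0.7 of the imbalance over the assumed range. Adjusting for the prior-year count removes most of that shift. Covariates less closely related to prior use remove less.

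**The case against.** The strongest reply is that nothing stated in the plan fails. A reader might infer that these outcomes have no pre-trial value at all, or that the adjustment in section 1.3.7 cannot be carried out. The documents support neither. Section 1.3.5.3.1 collects prescribed and over-the-counter laxative use at baseline. Section 1.3.7 speaks only of baseline data, not of the baseline value of each outcome. Section 1.3.4.1 names current bowel function and perceived constipation as covariates, and these can enter any of the models. That part of the reply stands.

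It can also be said that the plan nowhere states that the eligibility count will be discarded, and that the choice of covariates commonly belongs in an analysis plan. This is fair for prescriptions. It does not help for consultations, because the abstraction window leaves that value out.

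The size of the gain is open to challenge too. The correlation is assumed. Eligibility cuts the prior-year count off at three, which may lower r. In two arms diet and lifestyle come first, which may weaken the link between years. These points stand and are why the range starts at 0.3.

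Independent interrogation of prescribing databases (section 1.3.6.2) does protect identification. It does not protect consent, which comes afterwards. Chance imbalance alone does not bias a randomised contrast; the argument there is one of precision.

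Finally, the work is not nil. A wider window doubles the consultation period for 57 × 25 = 1,425 patients, or 57 × 30 = 1,710 if everyone expected to consent is covered, and some of those records are on paper.

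**Conclusion.** The point holds as a missed improvement. No prior-year consultation value, and no record-based prior-year prescription count, is planned as a covariate for the record-based outcomes or for the relapse and NHS-cost measures built on them. The gap is complete for consultations. For prescriptions it is partial, since self-reported baseline use is a usable but weaker substitute.

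It is not a contradiction between sections, no stated number changes, and the primary outcome has its own baseline.

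The gain is about 9% to 49% of variance (intervals about 5% to 29% narrower) against no adjustment, for an assumed r of 0.3 to 0.7 that is equal at both levels, and less against the adjustment already planned. A reader might take the upper end as the expected benefit; the documents do not support that. The firmer reason to act is that consent follows randomisation, in a setting where the protocol itself expects willingness to take part to depend on attachment to medication.

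**What to change.** 1. In section 1.3.5.3.5, state that when the query is adapted, the laxative prescription count for the 12 months before recruitment is kept for each consenting participant. This is essentially free, because the query already reads that period.
2. In the same section and in Table 2, widen the consultation abstraction at W52 to the 12 months before as well as the 12 months after recruitment. This is cheap: the records are already being opened and section 1.3.9 seeks consent for access to them. The cost is extra abstraction time per record, including paper records.
3. In section 1.3.7, name the prior-year prescription count and prior-year consultation count as covariates in the corresponding prescription, consultation, relapse and NHS-cost models, alongside the baseline data already planned.

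The number of practices and the primary analysis stay as they are.

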1.3.5.4 Participants' pathways through trial

		Activity
1		Potential participants identified from computerised practice databases using simple electronic query to flag individuals receiving prescriptions for constipation (3 or more in previous 12 months).
2		Initial screen by practice to identify clear exclusions.
3		Written invitation sent by practice (facilitated by research team) to patient to participate in study. Contact details form and pre-paid envelope included for patients wishing to join the study included. Research team to contact patient to answer questions and explain about process for informed consent. Consent form posted to patient with pre-paid envelope. Self completion questionnaire and pre-paid envelope also sent. Control patients will receive their diary (including pre-paid envelope) at this point.
4	W^0	When consent form is returned the telephone baseline interview will be conducted. patient advised to expect contact from practice to arrange 'intervention start' appointment.
5	W^1	Appointment at practice – laxative prescription issued or diet and lifestyle intervention initiated. All patient information and baseline data destroyed by research team if patient notifies practice of their wish to withdraw from study.
6	W^2	One week reinforcement phone call from nurse to patients randomised to personalised diet and lifestyle advice
7	W^{3-4}	Intervention fidelity measure – a small sample of patients in the standardised and personalised intervention arms of the trial will receive a short postal questionnaire to ask about the diet and lifestyle advice.
8	W^5	One month reinforcement phone call from nurse to patients randomised to personalised diet and lifestyle advice
9	W^{12}	Three month follow up outcome assessment (postal questionnaire) and collection of cost data and personal levels of success (telephone interview)
10	W^{26}	Six month follow up outcome assessment (postal questionnaire) and collection of cost data and personal levels of success (telephone interview)
11	W^{52}	Twelve month follow up outcome assessment (postal questionnaire & 1-week symptom diary). Review of practice notes to abstract data on consultation rates and prescription patterns.

1.3.5.5 Blinding of outcome assessment

Health technology assessment is essentially a pragmatic activity conducted in normal clinical practice. It follows that blinding doctors, nurses and patients to treatment is not desirable (even if practicable – which would not be the case here, since the three interventions are visibly and demonstrably different) since it distorts normal clinical practice. In contrast, blinding of assessors is desirable because it minimises subjective bias towards a given treatment. Where practical considerations (e.g. size of research team) preclude concealment of allocation of treatment from those collecting data, highly structured data collection instruments can reduce the risk of bias in data recording and analysis. In this study, complete concealment of the allocation is likely to be impractical. However, the individuals responsible for the delivery of training in the dietary and lifestyle intervention, and for the collection of qualitative data on facilitators of and barriers to adherence to treatment protocol, will not reveal their experiences in respect of individual practices to those collecting and analysing patient outcome data.

1.3.6 Sampling design and implementation

1.3.6.1 Practice recruitment and randomisation

General practices in England and Scotland will be invited by letter to participate. Standard sample size calculations for a cluster randomised trial³¹ indicate that we will need to recruit 57 practices in total (1.3.6.3). This estimate is based on the number of patients likely to be available in the average-sized practice; if larger practices participate, the number of practices required may be slightly reduced. We will initially seek to include practices from local primary care research networks but may need to supplement with others, depending on take up. Practices agreeing to take part in the study will be randomised by computer to one of the three arms. We recognise that practices may have preferences with respect to allocation of interventions. We will make it very clear to the practices approached to participate in the LIFELAX study that allocation to intervention will be completely at random and that practice preferences cannot be taken into account. Randomisation will be carried out by an individual not otherwise involved in practice contact, or in data analysis.

1.3.6.2 Patient identification and recruitment

Two methods of patient identification were considered: incident and prevalent cases. Consultation rate data²¹ indicate that there would be only a small number of incident cases per year in any one practice. Moreover, these incident cases would, at least initially, be subject to more intensive medical investigation²³, which would militate against inclusion in the trial. Finally, we are aware of experiences of differential rates of patient identification across active and control arms of previous cluster randomised trials (e.g. the UK BEAM trial) and the potential for selection bias that results from such differential rates. This risk is greater when incident cases are being identified, and when responsibility for identification lies with the clinician. For these reasons, only prevalent cases (1.3.4.1), which will be retrospectively identified through computerised records, will be considered.

The identification process will be through an independent interrogation of practice prescribing databases, and will therefore not be subject to influence by the participating clinicians. We believe that this approach will minimise selection bias.

To spread practice workload, patient recruitment in each practice will be spread over four months. It would not be practicable to identify all (i.e. across all 57 practices) potentially eligible patients prior to practice randomisation and patient contact. The reason for this is that bowel symptoms may fluctuate in patients and a patient identified as 'constipated' at a given point in time may no longer be 'constipated' several months later. We expect that the delivery of the intervention to practices will extend over 10 months. Initial eligibility of patients will be based on receipt of 3 or more prescriptions for laxatives in the preceding 12 months (1.3.4.1). If the patient identification query were to be run in all practices at the beginning of this 10 month period and patients thus identified were to be 'banked' until the intervention was delivered in a specific practice, some of those identified might no longer meet eligibility criteria, while others by then meeting eligibility criteria would not be considered for inclusion.

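### The 12-month prescription count that decides eligibility is tied to the query date, not to practice allocation, so it may include prescriptions issued after clinicians knew their arm

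*Protocol*

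**What the plan says.** Protocol section 1.3.4.1 restricts the trial to prevalent cases, "defined in terms of those prescribed laxatives three or more times in the previous 12 months", found by an electronic query of repeat prescribing databases. Section 1.3.6.2 repeats the rule: "Initial eligibility of patients will be based on receipt of 3 or more prescriptions for laxatives in the preceding 12 months". Neither section says on what date the 12 months end, other than by reference to when the query is run.

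On the order of events, section 1.3.6.1 has practices randomised by computer once they agree to take part. Section 1.3.6.2 then states: "It would not be practicable to identify all (i.e. across all 57 practices) potentially eligible patients prior to practice randomisation and patient contact". It adds: "We expect that the delivery of the intervention to practices will extend over 10 months". It rejects a scheme in which "patients thus identified were to be 'banked' until the intervention was delivered in a specific practice", because eligibility would drift in the meantime. Within a practice, "patient recruitment in each practice will be spread over four months".

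The safeguard offered in section 1.3.6.2 is that identification is by a query independent of the practice "and will therefore not be subject to influence by the participating clinicians". Section 1.3.5.5 says that doctors and nurses are not blinded. Section 1.3.3.2 invites all primary care professionals in both advice arms, general practitioners included, to training.

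**The concern.** Section 1.3.6.2 itself names differential identification across arms as a known source of selection bias in cluster trials, and relies on the independent query to minimise it. An independent query prevents a clinician from choosing whom to put forward. It does not make the counted quantity independent of allocation, because the same clinicians issue the prescriptions. If part of the look-back falls after the practice knows its arm, and prescribing to patients not yet enrolled has shifted by then, membership of the eligible pool depends partly on allocation.

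The patients affected would be light users close to the threshold of three. If issues fell in the advice arms only, some of these patients would drop out of the pool there while similar patients remained in it in the laxative arm. Baseline covariates (sections 1.3.4.1 and 1.3.7) adjust for measured differences among those recruited. They cannot bring back patients whom the query never listed.

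**Working it through.** **Order of events.** The protocol gives no date for allocation or query in any practice. Three statements in section 1.3.6.2 bear on it: identifying everyone before randomisation is ruled out, banking an early list is rejected, and delivery is staggered over 10 months. Together they place each practice's query near delivery in that practice and, on the natural reading, after its allocation. Nothing in the protocol ends the count at allocation or requires the query to come before the arm is disclosed.

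**Share of the window exposed.** If the query follows allocation by L months, the share of the 12-month window after allocation is L/12. The lag is not stated, so three values are assumed:
- 1 month: 1/12 = 8%.
- 4 months, the length of recruitment within a practice (relevant if the query were repeated during it, which the protocol neither says nor excludes): 4/12 = 33%.
- 10 months, possible only if all practices were allocated at the start of the roll-out: 10/12 = 83%.

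**Effect on eligibility.** Assume Poisson counts with r prescriptions a year and a proportional cut c in issues after allocation. The expected count in the window is λ = r × [(12 − L) + L(1 − c)]/12, and P(3 or more) = 1 − e^(−λ)(1 + λ + λ²/2). Only the threshold of 3 and the 12-month window come from the protocol; r, c and L are assumptions.

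Worked case, r = 4 and c = 0.25:
- No change: λ = 4, P = 0.762.
- L = 1: λ = 4 × 11.75/12 = 3.917, P = 0.749.
- L = 4: λ = 4 × 11/12 = 3.667, P = 0.709.
- L = 10: λ = 4 × 9.5/12 = 3.167, P = 0.613.

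Over the range (each cell gives P for a 25% cut, then a 50% cut):

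| Rate per year | No change | L = 1 | L = 4 | L = 10 |
|---|---|---|---|---|
| 3 | 0.577 | 0.563, 0.548 | 0.519, 0.456 | 0.424, 0.256 |
| 4 | 0.762 | 0.749, 0.736 | 0.709, 0.647 | 0.613, 0.413 |
| 6 | 0.938 | 0.932, 0.926 | 0.912, 0.875 | 0.853, 0.679 |
| 12 | 0.999 | 0.999, 0.999 | 0.999, 0.997 | 0.996, 0.970 |

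At a one-month lag the largest fall in the table is 0.577 − 0.548 = 0.029. Patients on monthly prescriptions qualify almost regardless.

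**Sample size.** The stated 57 practices reproduces. A difference of 0.3 SD with 90% power at two-sided 5% needs 234 per arm. The design effect is 1 + 24 × 0.04 = 1.96, and 234 × 1.96 = 458.6. Dividing by 25 gives 18.3, so 19 practices per arm and 57 in all. The end date of the look-back does not enter this calculation.

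**The case against.** The best defence is that nothing shows a long lag. Ruling out a single up-front query across all 57 practices does not fix the order or the gap within one practice. Section 1.3.6.1 allows recruitment to be supplemented according to take-up, which is compatible with allocating practices as they join. With banking rejected, the query may follow allocation by weeks. This stands, and it limits the size of the point.

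The mechanism can also be doubted. Section 1.3.3.1 makes diet and lifestyle first-line only for patients allocated to those arms, who may continue laxatives if required. Section 1.3.5.3.1 withholds the intervention until the practice has the signed consent form. No passage asks a practice to change prescribing for anyone else. The query reads repeat prescribing databases, and a repeat issue is not plainly a fresh decision. All of this stands. What remains is that spill-over from a trained practice is plausible: section 1.3.1 justifies cluster randomisation by the risk that professionals give elements of the package to patients not assigned to it.

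A reader might infer three stronger things, none supported by the protocol. First, that the lag runs up to 10 months: that figure is the roll-out of delivery, not the interval from allocation to query. Second, that practices in the laxative arm would issue more prescriptions because they are reminded of dose ranges: the reminder in section 1.3.3.1 concerns dose, not the number of issues. Third, that the arms will differ before baseline: the text shows only that the route is open.

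**Conclusion.** The point holds as a gap in the eligibility definition and as an overstated assurance. The count is not anchored to allocation, and the query appears to follow randomisation. The claim of no clinician influence is therefore true of running the query but not of the prescriptions counted.

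The size is unknown. It is negligible if the query follows allocation by weeks. It becomes material only if the lag is many months and prescribing to patients not yet enrolled also changes by arm, and the protocol states neither. The figures for longer lags show how sensitive the rule would be and do not predict what will happen. No effect on the quality-of-life outcome has been shown. The change is still worth making, because the protocol sets no limit on the lag and closing the route costs little.

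**What to change.** In section 1.3.6.2, adopt one of two rules for every practice:
- run the query immediately before the practice's allocation is disclosed, and recruit from that list throughout the four months; or
- end the 12-month count on the practice's allocation date, whenever the query is run or repeated.

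Allocate each practice when its roll-out slot comes up. The window then stays recent, which respects the protocol's sound reason for not banking patients. State the end date in section 1.3.4.1 as well. Confine the statement about clinician influence to the running of the query, or extend it to the prescriptions counted once the window is anchored.

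The cost is one date parameter or one scheduling step, and a sentence or two of text. The 57 practices are unchanged. The small downside is that patients who first reach three prescriptions after allocation are not invited.
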